## **9.5 Analysis of secondary variables**

### **9.5.1 Efficacy / Pharmacodynamics**

Summary statistics for the secondary endpoints and their changes from baseline will be provided by treatment group and visit/time. Corporate Confidential Information

A longitudinal analysis of the secondary PD endpoints may be performed if deemed relevant. Graphical displays of mean time profiles may be constructed as appropriate.

### **9.5.2 Safety**

#### **Adverse events**

All information obtained on adverse events will be listed by treatment group and subject. Time since start of IVT injection will be indicated in the listing.

The number and percentage of subjects with adverse events will be listed by treatment group, body system and preferred term. Ocular adverse events will be tabulated and summarized by study eye vs. fellow (non-study) eye. A subject with multiple adverse events within a body system or preferred term is only counted once towards the total of this body system or preferred term

Corporate Confidential Information

#### **Concomitant medications / Significant non-drug therapies**

All concomitant therapies will be listed by treatment group and patients.

### **9.5.3 Health-related quality of Life**

Not applicable.

### **9.5.4 Pharmacokinetics**

Corporate Confidential Information

### **9.5.5 Pharmacogenetics /pharmacogenomics**

Corporate Confidential Information

**9.5.6 Other assessments**

Corporate Confidential Information

Corporate Confidential Information

**9.5.7 PK/PD**

Not applicable.

**9.5.8 Ocular assessments**

Corporate Confidential Information

Ocular assessments will be listed by treatment group and patients.

Summary statistics of ocular assessments will be provided by treatment group and visit/time point.

**9.7 Power for analysis of key secondary variables**

Not applicable .

**9.8 Interim analyses**

Corporate Confidential Information

## 10 Ethical considerations

### 10.1 Regulatory and ethical compliance

This clinical study was designed and shall be implemented and reported in accordance with the ICH Harmonized Tripartite Guidelines for Good Clinical Practice, with applicable local regulations (including European Directive 2001/20/EC, US Code of Federal Regulations Title 21, and Japanese Ministry of Health, Labor, and Welfare), and with the ethical principles laid down in the Declaration of Helsinki.

### 10.2 Informed consent procedures

Eligible patients may only be included in the study after providing written (witnessed, where required by law or regulation), IRB/IEC-approved informed consent, or, if incapable of doing so, after such consent has been provided by a legally acceptable representative of the patient. In cases where the patient's representative gives consent, the subject should be informed about the study to the extent possible given his/her understanding. If the patient is capable of doing so, he/she should indicate assent by personally signing and dating the written informed consent document or a separate assent form. Informed consent must be obtained before conducting any study-specific procedures (i.e., all of the procedures described in the protocol). The process of obtaining informed consent should be documented in the patient source documents.

Novartis will provide to investigators in a separate document a proposed informed consent form that complies with the ICH GCP guideline and regulatory requirements and is considered appropriate for this study. Any changes to the proposed consent form suggested by the investigator must be agreed to by Novartis before submission to the IRB/IEC, and a copy of the approved version must be provided to the Novartis monitor after IRB/IEC approval.

Corporate Confidential Information

In the event that Novartis wants to perform testing on the samples that are not described in this protocol, additional Institutional Review Board and/or ethics committee approval will be obtained.

### 10.3 Responsibilities of the investigator and IRB/IEC

The protocol and the proposed informed consent form must be reviewed and approved by a properly constituted Institutional Review Board (IRB) before study start. A signed and dated statement that the protocol and informed consent have been approved by the IRB must be given to Novartis before study initiation. Prior to study start, the investigator is required to sign a protocol signature page confirming his/her agreement to conduct the study in accordance with these documents and all of the instructions and procedures found in this

protocol and to give access to all relevant data and records to Novartis monitors, auditors, Novartis Clinical Quality Assurance representatives, designated agents of Novartis, IRBs, and regulatory authorities as required. If an inspection of the clinical site is requested by a regulatory authority, the investigator must inform Novartis immediately that this request has been made.

## **10.4 Publication of study protocol and results**

Upon study completion and finalization of the study report the results of this trial may be submitted for publication and/or posted in a publicly accessible database of clinical trial results.

## **11 Protocol adherence**

Investigators ascertain they will apply due diligence to avoid protocol deviations. Under no circumstances should the investigator contact Novartis or its agents, if any, monitoring the trial to request approval of a protocol deviation, as no authorized deviations are permitted. If the investigator feels a protocol deviation would improve the conduct of the study this must be considered a protocol amendment, and unless such an amendment is agreed upon by Novartis and approved by the IRB it cannot be implemented. All significant protocol deviations will be recorded and reported in the CSR.

### **11.1 Protocol Amendments**

Any change or addition to the protocol can only be made in a written protocol amendment that must be approved by Novartis, Health Authorities where required, and the IRB. Only amendments that are required for subject safety may be implemented prior to IRB approval. Notwithstanding the need for approval of formal protocol amendments, the investigator is expected to take any immediate action required for the safety of any subject included in this study, even if this action represents a deviation from the protocol. In such cases, Novartis should be notified of this action and the IRB at the study site should be informed within 10 working days.

## 13 Appendix 1: Blood collection log: blood sampling schedule for safety, PG, PK, PD, and immunogenicity

## 14 Appendix 2: Sample labeling and shipping information

### 14.1 Sample labeling

The Sample Numbers are reported in [Section 13-Appendix 1](#).

The subject ID, exact clock time of dosing, as well as actual sample collection date and time will be recorded using a 24-hour clock on the appropriate blood collection summary page of the eCRFs. Sampling problems will be noted in the Notes field of the eCRFs.

Examples of sample labels for different sample types are presented below.

#### Sample labeling for serum PK sample

The sample label is to include the following information:

Study Code:	LFG316A2204
Subject Number:	5101
Sample Number:	Sample 1 XX (sernm) (ex. 110 (serum))
Vial indicator:	A or B (because resulted serum is to be split into 2 vials)
Required Timepoint:	ex. Pre-injection (or other predetermined timepoints)
And/ Or Study Day:	ex. Day 1
Time:	hh:mm (24 hours format)
Date:	dd-Mmm-YY (ex. 18-Aug-11)

#### Sample labeling for serum PD samples (total CS assay)

The sample label is to include the following information:

Study Code:	LFG316A2204
Subject Number:	5101
Sample Number:	Sample 2XX (sernm) (ex. 201 (serum))
Vial indicator:	A or B (because resulted serum is to be split into 2 vials)
Required Timepoint:	ex. Pre-injection (or other predetermined timepoints)
And/ Or Study Day:	ex. Day 1
Time:	hh:mm (24 hours format)
Date:	dd-Mmm-YY (ex. 18-Aug-11)

## Sample labeling for serum immunogenicity samples

The sample label is to include the following information:

Study Code:	LFG316A2204
Subject Number:	5101
Sample Number:	Sample 1:XX (eg 101 serum)
Vial indicator:	A or B (because resulted setllll is to be split into 2 vials)
Required Timepoint:	ex. Pre-injection (or other predetermined timepoints)
And/ Or Study Day:	ex. Day 1
Time:	hh:mm (24 hours format)
Date:	dd-Mmm-YY (ex. 01-Oct-11)

## 14.2 Sample shipment instructions

For each shipment, an inventory of the samples should accompany the shipment. This inventory should include the study ID, subject ID, sample number, visit number, and scheduled time of collection.

Clearly indicate any missing specimens. The original inventory will be retained at the site in the Investigator's file.

All samples will be kept at the temperature specified up to and during the shipment. Unless instructed otherwise, the samples will be packed carefully with suitable packing material and dry ice to keep them frozen.

All shipments should be sent (Monday through Wednesday **only**) by a carrier guaranteeing overnight delivery. The following items should be considered:

- Advise the carrier of the type of service desired, need for personalized door-to-door pickup, and delivery guaranteed within 24 hours.
- Advise the carrier of the nature of the shipment's contents (human biological specimens) and label the package accordingly.
- Indicate Novartis drug code and Study No. on the face of the parcel to be shipped. The parcel also must carry a "dangerous goods" label because of the dry ice (labels supplied by the courier).
- The carrier must be asked to store the parcel(s) in a freezer if shipment is delayed and to replace exhausted dry ice before transportation continues.
- Shipping reservations should be made to allow delivery to Novartis before 16:00 (4 pm) local time Monday to Thursday and before 11:00 (11 am) local time on Friday. Shipments should not be sent between Thursday and Sunday, to prevent arrival over the weekend.

#### **14.2.1 Instructions for shipment of PK, PD, PG, and immunogenicity samples to the central lab**

All study samples (PK, PD, PG, and immunogenicity) will be first sent from the study clinics to the central lab for initial storage pending scheduled batch shipments to the appropriate analytical lab. Samples should be sent to the following address-unless otherwise directed by Corporate Confidential Information

For each shipment, an inventory of the samples should accompany the shipment. This inventory should include the study ID, subject ID, sample number, visit number, scheduled time of collection.

Additional information will be provided by the central lab manual.

Clearly indicate any missing specimens. The original inventory will be retained at the site in the Investigator's file.

All samples will be kept at the temperature specified up to and during the shipment. Samples have to be packed according to the ICAO/IATA-Packing-Instructions in an insulated box. To guarantee that the samples remain deep frozen during transport, use about **10 kg of dry ice** per box which will keep the samples frozen during the whole duration of the transport (air freight). One aliquot of samples will be shipped to the designated Laboratory. The remaining aliquots will be shipped to the same address after assurance that the first aliquots arrived in good condition.

**Please notify the addressee above *in advance* of the shipment and indicate:**

- The time and date of shipping and approximate time of arrival,
- To whom the shipment is addressed, the study number, the name of the contact and the shipping form number (or equivalent airbill number),
- The sender's name, telephone number and alternative contact personnel,
- The total number of samples, number of matrices if applicable, and number of cartons and unit weight of each carton.

Also notify the Clinical Trial Leader at Novartis when a shipment has been scheduled.

#### **14.2.2 Instructions for shipment of PK, PD, and immunogenicity samples from central lab to the bioanalytical lab**

All PK, PD, and immunogenicity specimens will be kept at the temperature specified in the PK, PD, and immunogenicity sample collection and processing sections until shipment.

Samples have to be packed according to the ICAO/IATA-Packing-Instructions in an insulated box. To guarantee that the samples remain deep frozen during transport, use about **10 kg of dry ice** per box which will keep the samples frozen during the whole duration of the transport (air freight).

Please notify the analytical lab contact person *in advance* of the shipment.

A shipping log must be included with the shipment. Samples should be shipped with dry ice (use about 10 kg of dry ice per box).

Selection of the bioanalytical lab is ongoing and will be communicated to the central lab once it is finalized.

**Please notify the addressee *in advance* of the shipment and indicate:**

- Number of the airbill,
- The time and date of shipping and approximate time of arrival,
- Flight Number,
- To whom the shipment is addressed, the study number, carrier and the shipping form number (or equivalent airbill number),
- The sender's name, telephone number and alternative contact personnel,
- The total number of cartons and unit weight of each carton.

Also notify the Clinical Trial Leader at Novartis when a shipment has been scheduled.

The samples should be sent at the beginning of a week in order to arrive not later than Thursday.

## 1 Introduction to RAP documentation

### 1.1 Scope

The RAP documents contain detailed information to aid the production of Statistics & Programming input into the Clinical Study Report (CSR) for trial “**CLFG316A2204**”.

**Module 3 (M3) provides the description of the statistical methodology** used to analyze the data, **Module 7 (M7)** details the presentation of the data, including shells of summary tables, figures and listings, and **Module 8 (M8)** contains programming specifications e.g. for derived variables and derived datasets, to support the creation of CSR outputs.

### 1.2 Changes to RAP documentation (M3)

Refer to corresponding guidances and NIBR RAP Addendum template for detailed information on the requirements of documenting changes to RAP documentation.

**For the statistical methodology (M3)**, any major changes occurring before database lock to the statistical methodology should be reflected in the RAP M3 documentation via version control (new document version to be approved by the trial team as the original module).

Major changes include, but are not limited to, changes in protocol that affect study design and statistical methodology.

Minor changes to the RAP M3 documentation can be captured e.g. by a study note to file / note in RAP Addendum or within the CSR itself. Minor changes include, but are not limited to, change in statistical model. Corrections of typographical errors or modification of spelling (from English to American, for example) do not need to be incorporated into the RAP M3 documentation.

Corporate Confidential Information

---

Corporate Confidential Information

Corporate Confidential Information

## 2 Study objectives and design

### 2.1 Study objectives

#### 2.1.1 Primary objective(s)

- To assess the effect of intravitreal LFG316 Corporate Confidential Information on the protocol-defined, Day 85 response rate in the study eye of patients who meet the inclusion criteria.

The above objective applies to the study eye only.

#### 2.2.2 Secondary objective(s)

- To assess the safety and tolerability of intravitreal LFG316 Corporate Confidential Information in patients who meet the inclusion criteria. Corporate Confidential Information
- To assess the effect of intravitreal LFG316 Corporate Confidential Information on vitreous haze as measured on the Nussenblatt scale, ETDRS visual acuity, macular edema, presence or absence of chorioretinal lesions, and anterior chamber cells score in eyes with active NIU, in at least one eye, requiring intensification of systemic immunosuppressive therapy, and compared between Baseline and Days 2, 8, 15, 29, 43, 57, and 85. Corporate Confidential Information
- To evaluate the serum concentrations of total LFG316 and total C5 during the course of the study.

The above objectives apply to the study eye only.

Corporate Confidential Information

- 

## Corporate Confidential Information

### 2.2 Study design and treatment

This is a multi-center, randomized, active-controlled, open-label, proof-of-concept study. The study will be carried out at ocular inflammation specialty clinics in the US and UK. Approximately 24 patients with active NIU in at least one eye, requiring intensification of systemic immunosuppressive therapy will be enrolled and randomized in a 2:1 ratio to receive:

- LFG316 Corporate Confidential Information administered intravitreally (n=16)

Only one eye (designated as the study eye) will be dosed per patient. If either eye would qualify as the study eye, one eye will be selected as the study eye during the screening period based on the following criteria:

- Higher vitreous haze score
- If not determined by vitreous haze score, then by lower visual acuity
- If not determined by visual acuity, investigator preference.

Throughout the study, the fellow eye (i.e., non-study eye) should be examined and treated at the investigator's discretion. Efficacy assessments (visual acuity and eye exams) will be conducted by a clinician masked to treatment condition.

For patients randomized to LFG316, three successive doses will be administered on Days 1, 29, and 57. First dose (Day 1) may occur within 0-14 days of Screening. After first dose, safety, efficacy, and PK assessments will occur at 6 scheduled visits over a 12-week period.

## Corporate Confidential Information

However, patients can attend for unscheduled visits as needed and as determined by the investigator. Patients will be monitored for safety and ocular assessments obtained throughout treatment and follow-up periods. Patient eligibility will be assessed as outlined in Figure 2-1 below. An overall study scheme is shown in Figure 2-2 below.

Ocular assessments include:

- Best corrected visual acuity (ETDRS)
- Intraocular pressure (IOP)
- Slit lamp biomicroscopy
- Dilated ophthalmoscopy
- Standardized vitreous haze score (Nussenblatt et al 1985)
- Color fundus photos\*
- Spectral domain optical coherence tomography (sd-OCT)\*
- Anterior chamber cells
- Chorioretinal lesions (absent/present per PI investigator)
- Vasculitis (absent or present per Investigator)

- Presence of chorioretinal infiltrates due to uveitis
- Macular edema due to uveitis (absent or present per Investigator)

\*: sd-OCT images and color fundus photos are only checked for quality and archived.

**Corporate Confidential Information**

**Figure 2-2 Overall study scheme**

Corporate Confidential Information

Visit	Screening Period	Treatment Period							
		1	2	3	4	5	6	7	8
Day	-14 to -1	1	2	8	15	29	43	57	
LFG316 5 mg Intravitreal administration (n=16)		X				X		X	

Corporate Confidential Information

Corporate Confidential Information

For assessment details, refer to the assessment schedule in protocol.

### **3 First interpretable results (FIR)**

Corporate Confidential Information

### **4 Interim analyses**

Corporate Confidential Information

## Corporate Confidential Information

### **5 Statistical methods: Analysis sets**

Patients will be analyzed and reported based on the treatment received.

All patients who received study drug Corporate Confidential Information will be included in the safety analysis set.

All patients in the safety analysis set with evaluable PK data and with no major protocol deviations that have an impact on PK data will be included in the PK analysis set.

All patients in the safety analysis set with evaluable PD data (Total C5) with no major protocol deviations that have an impact on PD data will be included in the PD analysis set.

All patients in the safety analysis set who receive any study treatment Corporate Confidential Information with evaluable efficacy data for at least one efficacy endpoint/s (ocular assessments) and with no major protocol deviations that have an impact on efficacy data will be included in the first efficacy (Efficacy 1) analysis set. For the Efficacy 1 analysis set, any patient who discontinues after receiving at least one dose of study drug will be included up to the time of discontinuation or until the time they received rescue medication.

All patients in the safety analysis set who receive any study treatment Corporate Confidential Information with evaluable primary efficacy endpoint (response rate and remission rate on Day 85) and with no major protocol deviations that have an impact on the primary efficacy endpoint will be included in the second efficacy (Efficacy 2) analysis set.

Corporate Confidential Information

Corporate Confidential Information

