## Corporate Confidential Information

**Sample size determination**

The target sample size for this study is approximately 24 patients, randomized in a 2:1 ratio

Power calculations are not based

upon a comparison between LFG316 Corporate Confidential Information but rather on the null hypothesis that the response rate in the LFG316 arm (PLFG) will not differ from the lower bound of the expected Corporate Confidential Information response rate which is assumed to be 60%. With 16 patients in the LFG316 arm, the null hypothesis  $H_0: PLFG \leq 0.60$  will be rejected in favor of  $H_1: PLFG > 0.60$ , if 11 / 16 patients in the sample are responders. Such a rejection rule has 17% false positive rate (incorrectly reject  $H_0$  when it is true) and 45% (80%, 92%) power to correctly reject  $H_0$  when the true PLFG is 70% (80%, 85%).

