## 5.5.6      **Rescue**

### 5.5.6.1    **Rescue of study eye**

For any patients who meet the following criteria in the study eye, the study mug will be discontinued, and conventional therapy instituted:

- Loss of >10 letters in best corrected visual acuity (BCVA) at any visit, as compared to baseline that in the opinion of the investigator is due to worsening of uveitis.
- Active vitritis, anterior chamber inflammation, or chorioretinitis 28 ± 3 days after their last dose that, in the opinion of the investigator, is significantly worse as compared to the previous visit and requires alternate therapy
- Unilateral flare in fellow / non-study eye which does not respond to local treatment (including ozurdex® implant) or bilateral flare in both eyes which require the intensification of systemic immunosuppressive therapy.

Patients who are rescued will be asked to attend the per protocol visit schedule for the remainder of the trial in order to be followed up for safety.

Corporate Confidential Information

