### 5.5.6.2    **Rescue of fellow eye**

The investigator will care for the fellow eye at his or her discretion. There are no restrictions on topical, periocular, or intravitreal therapy in the fellow eye other than those noted in [Section 5.5.7; Table 5-1](#).

NOTE: If during the trial, a patient requires systemic immunosuppressive therapy for the fellow eye, investigational therapy for the study eye should be stopped and conventional therapy instituted. The patient should continue in the study for assessment purposes. Patients who require systemic immunosuppressive therapy may be replaced to maintain adequate study power if the treatment was implemented for the sole purpose of treating the fellow eye.

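### In the readable SAP, neither efficacy set counts a study-eye rescue as a Day 85 failure of LFG316, and each way of filling the gap raises the response rate

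*SAP*

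**What the plan says.** SAP Section 7.1 reports the Day 85 response and remission rates on both Efficacy 1 and Efficacy 2, with Efficacy 1 of primary interest. Section 5 treats rescue differently in the two sets:

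- **Efficacy 1.** A patient who discontinues after at least one dose "will be included up to the time of discontinuation or until the time they received rescue medication".
- **Efficacy 2.** Treated patients "with evaluable primary efficacy endpoint (response rate and remission rate on Day 85") and without a major deviation affecting that endpoint. The readable definition does not mention rescue.

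Table 5-2 removes from Efficacy 2 any patient with deviation M01, use of prohibited medication. M01 is not listed for Efficacy 1.

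The protocol expects examinations after rescue. Under 5.5.6.1, study-eye rescue stops study drug and starts conventional therapy, and "Patients who are rescued will be asked to attend the per protocol visit schedule for the remainder of the trial", with safety follow-up as the stated purpose. Under 5.5.6.2, for systemic therapy needed by the fellow eye, "The patient should continue in the study for assessment purposes". Protocol Section 6 asks patients who stop LFG316 before Day 85 to attend all remaining visits.

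SAP 7.1 makes a patient a responder on any one criterion, and its missing-data rules do not mention rescue. SAP 7.4 says that missing values are not imputed.

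**The concern.** A patient rescued because the study eye worsened is a treatment failure in the ordinary sense, and the trial asks what LFG316 achieves by Day 85. The readable plan has no rule that records this outcome as a non-response in either set. The patient's status is either lost or taken from an examination made on the therapy that replaced LFG316.

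The reported result is a single-arm rate with a 90% exact interval, set against 60%, in about 16 patients. At that size, the handling of a few rescued patients can move the rate from below the benchmark to well above it. Because both sets lack the rule, agreement between them would not show that rescue had been handled soundly.

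**Working it through.** **The plan's own figures.** The protocol synopsis (Sample size determination) starts "With 16 patients in the LFG316 arm", takes a benchmark "response rate which is assumed to be 60" percent, rejects "if 11 / 16 patients in the sample are responders", and states "Such a rejection rule has 17% false positive rate". With X ~ Bin(16, p), P(X ≥ 12) is 0.167 at p = 0.60, and 0.450, 0.798 and 0.921 at 0.70, 0.80 and 0.85. These match the stated 17% and 45% (80%, 92%). Read as at least 11 of 16, the rule gives 0.329 at p = 0.60. The stated figures therefore need at least 12 responders, and I use 12 below. That mismatch is a separate matter.

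**What happens to a study-eye rescue at Day 85**

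| Set and reading | Day 85 status | Effect on the rate |
|---|---|---|
| Efficacy 1 | Data end at rescue, so all Day 85 parameters are missing; SAP 7.1 then sets the status to missing, and 7.4 does not impute | Failure appears to leave the denominator |
| Efficacy 2, rescue not coded M01 | Observed status on conventional therapy | Responder if any one criterion is met |
| Efficacy 2, rescue coded M01 | Patient excluded | Failure leaves the denominator |

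**Illustration.** The rescue rate, the response without rescue and the response after rescue are all assumptions. Let n = 16, r be the number rescued, a = 0.75 the response without rescue, and s the response after rescue.

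- Rescue as failure: a(n − r)/n
- Rescued patients excluded or missing: a
- Observed status used: [a(n − r) + s·r]/n, which exceeds rescue-as-failure by s·r/n

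| r | Rescue as failure | Excluded or missing | Observed, s = 0.2 | s = 0.4 | s = 0.6 |
|---|---|---|---|---|---|
| 2 | 65.6% | 75% | 68.1% | 70.6% | 73.1% |
| 4 | 56.3% | 75% | 61.3% | 66.3% | 71.3% |
| 6 | 46.9% | 75% | 54.4% | 61.9% | 69.4% |

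With r = 4, rescue as failure is 0.75 × 12/16 = 9/16. Using observed status adds 4s/16, which is 5, 10 or 15 points. Exclusion adds 0.75 × 4/16, about 19 points.

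**Effect on the reported statistics, r = 4.** The chance of at least 12 responders of 16 comes from adding Bin(12, 0.75) and Bin(4, s). With rescue as failure it is 0.75^12 = 0.032. With observed status it is 0.156, 0.315 and 0.494 for s = 0.2, 0.4 and 0.6.

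For one concrete outcome, let 9 of the 12 patients not rescued respond:

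| Handling of the 4 rescued | Rate | 90% Clopper-Pearson interval | Exact one-sided p against 60% |
|---|---|---|---|
| Failures | 9/16 = 56.3% | 33.3% to 77.3% | 0.716 |
| Observed, 2 improved | 11/16 = 68.8% | 45.2% to 86.8% | 0.329 |
| Excluded or missing | 9/12 = 75.0% | 47.3% to 92.8% | 0.225 |

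**The case against.** A reader might infer that a rescued patient who improves will be counted as an LFG316 responder in Efficacy 2. The documents do not establish that. Protocol Table 5-1 prohibits new systemic steroids or immunomodulators in the LFG316 arm, and new topical, periocular or intravitreal steroid in the study eye. Section 5.5.8 says that a patient needing a prohibited treatment should be withdrawn. Read with M01, these passages plausibly remove rescued patients from Efficacy 2, which would make it a per-protocol type of set. This stands as a limit on the claim, but it does not cure the problem: exclusion takes failures out of the denominator, and in the illustration it raises the rate more than crediting does.

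Text is redacted after the set definitions and after the study-eye rescue rules, so a scoring rule could exist there. That also stands.

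The size is uncertain. A 60% response after rescue may be generous. Response is measured from baseline, so a patient rescued for losing more than 10 letters would have to regain more than 20 to qualify on acuity. Any other single criterion would still suffice. The lower values of s allow for this.

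Remission is largely protected, because it requires being off all immune modulatory therapy with no worsening during the trial. Exclusion under M01 would still shrink its denominator.

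Finally, nothing describes Efficacy 2 as a formal check on Efficacy 1, and the SAP says that no decision should rest on the p-value. The rate and interval remain the reported primary result, and Efficacy 1, the set of primary interest, has the same gap.

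**Conclusion.** The point holds in this form: the readable SAP never scores a study-eye rescue as a Day 85 non-response. Efficacy 1 appears to set it to missing. Efficacy 2 either takes the observed status on conventional therapy or excludes the patient, depending on an M01 coding choice that the documents leave open. Each route raises the LFG316 response rate relative to counting rescue as failure, unless no rescued patient would meet a response criterion and observed status is used.

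With 4 of 16 rescued and 75% response otherwise, the excess is about 5 to 15 points if observed status is used and about 19 points if rescued patients drop out of the denominator. These sizes rest on assumed rescue and response rates and on there being no contrary rule in the redacted text. The stronger conclusion, that Efficacy 2 necessarily credits LFG316 with the effect of rescue therapy, is not supported.

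**What to change.** In SAP Sections 5 and 7.1, for both Efficacy 1 and Efficacy 2:

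- State that a patient who received rescue therapy because of the study eye before the Day 85 assessment stays in the denominator and is scored non-responder and non-remission at Day 85.
- State that such rescue under protocol 5.5.6 does not by itself trigger exclusion under M01.
- For systemic therapy started solely for the fellow eye, set Day 85 status to missing in both sets, report the number of such patients, and add a sensitivity analysis counting them as non-responders.

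Protocol 5.5.6.1 (which lists fellow-eye flare under study-eye rescue), 5.5.6.2, Table 5-1 and 5.5.8 must be reconciled, so that it is clear which patients stay in follow-up and which eye prompted the rescue. How they are reconciled is a matter for the sponsor.

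The cost is a few sentences in the SAP, one derived flag based on treatment and visit data that the protocol already collects, and one short sensitivity table. The downside is that the reported response rates may be lower.
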